### **Exclusion criteria:**

1. Severe alcoholic hepatitis defined as Maddrey's discriminant function  $>32$
2. Patients with other concomitant liver diseases:
  - a. Hepatitis B
  - b. Hepatitis C
  - c. Non-alcoholic fatty liver disease (NAFLD)
  - d. Autoimmune hepatitis (AIH)
  - e. Hereditary hemochromatosis
3. Patients who are obese (a BMI of  $30 \text{ kg/m}^2$  or more) and with metabolic syndromes
4. Patients with bleeding disorders and who have been on anticoagulant or antiaggregant treatments
5. Patients who have been on corticosteroid therapy or pentoxifylline for alcoholic hepatitis
6. Patients with hepatocellular carcinoma
7. Pregnant patients
8. Patients who are breastfeeding
9. Patients with Childs C liver cirrhosis
10. Patients who have pyridoxine allergy or history

11. Patients who are judged by investigator that participation of the study is difficult due to disease as follow; hepatic cirrhosis, Wilson's disease, malignant tumor, serious metabolic disease, severe renal disease, severe pulmonary disease, severe cardiovascular disease, severe nervous disease/psychiatric disorder, muscle disease and etc
12. Patients taking vitamin E, herbal supplements, or other investigational products within 90 days prior to the participation in the study.
13. Patients who have been taken any medications that could affect the treatment: hypoglycemic agents, colchicine, penicillamine, corticosteroids, ursodeoxycholic acid, pentoxifylline, long-term use of NSAIDs, statins, neuroleptics, anticonvulsant medications, high-dose acetaminophen( $\geq 2.5$ g/day)
14. Patients who have received treatment that may affect liver function within 1 month prior to the participation in the study
15. Patients who could not comply with alcohol abstinence.
16. Patient who considered ineligible for participation in the study as Investigator's judgment

**Note:** Patients enrolled in this study MUST abstain from alcohol consumption throughout the study period

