Apart from a reliable history of significant alcohol intake, no single laboratory or imaging testing can definitively confirm the diagnosis of ALD. Hence, its diagnosis is based on the compilation of clinical findings of hepatomegaly with signs of chronic liver disease, radiographic evidence of liver steatosis, fibrosis or cirrhosis, combined with abnormal biochemical results suggestive of liver injury [11].

Meanwhile, NAFLD is closely linked to obesity, caused by excessive food intake with a high-calorie, high-fat diet combined with a sedentary lifestyle [12, 13]. Most often, it is also associated with metabolic dysfunction [11, 14]. Obese people are more likely to develop

metabolic syndrome, and nonalcoholic fatty liver disease (NAFLD) has been identified as the hepatic manifestation of metabolic syndrome [15].

Therefore, in the context of this study, we propose to exclude the subjects who are obese (a body mass index (BMI) of 30 kg/ m^2 or higher) and with metabolic syndrome (based on the harmonised criteria) to minimise the risk of misclassification between AFLD and NAFLD.

Clinical evidence of decompensated liver disease such as ascites and its severity, hepatic encephalopathy; severity according to West Haven criteria, jaundice and coagulopathy must be assessed for. Evidence of alcoholic hepatitis as demonstrated by hepatocellular transaminitis of AST:ALT > 2:1 due to deficiency of pyridoxal 5'phosphate level in alcoholic patients, raised gamma glutamyl transpeptidase (GGT) raised mean corpuscular volume (MCV), raised total bilirubin with severely ill patients having coagulopathy as demonstrated by raised international normalised ratio (INR) and prothrombin time (PT). Patients with other forms of bleeding disorder, as well as those on anticoagulant or antiaggregant treatments are not eligible to participate in the trial. Patients who have been taking vitamin E, herbal supplements or other investigational products are also excluded.

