Tocotrienols are generally safe and are usually well tolerated. By participating in this research, it is possible that the treatment given to the subjects may or may not help improve their liver function. There is a risk that their condition will not get better and that the intervention won't work. The treatment given to them are usually in low doses and are unlikely to cause serious side-effects. However, in patients with bleeding disorders, tocotrienols might slow blood clotting. Tocotrienols may also interact with "blood thinners" such as warfarin and antiaggregants like aspirin, increasing the risk of bleeding. Thus, we advise against taking the treatment with these medications. Symptoms like nausea, diarrhea, stomach cramps, tiredness, dizziness, and blurred vision may rarely occur in cases of overdose. Allergic reactions to this supplement are rare; however, if they develop any symptoms of a serious allergic reaction, including rash, itching or swelling (especially of the face, tongue, or throat), dizziness, or trouble breathing, they should tell the doctor and get medical help right away. Venous blood taking would require a needle to pierce through their skin, which might also result in bruising and mild pain.

This trial will be conducted in compliance with the protocol, GCP and the applicable regulatory requirement(s). The population to be studied is adult patients aged 18-65 years, with a history of alcohol use disorder, who could comply with alcohol abstinence, and those with diagnosis of AFLD with lab evidence of Alcoholic Steatohepatitis (AST:ALT >2.0, elevated GGT) who come for follow up in Gastroenterology & Hepatology clinic in Hospital Canselor Tuanku Muhriz UKM (HCTM). Additionally, our research subjects were also recruited from the general public who responded to our recruitment poster on social media platforms.

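### Exclusion item 4, read literally, excludes only patients with both a bleeding disorder and anticoagulant or antiaggregant use, whereas the Project Synopsis makes either one disqualifying

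*Protocol*

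**What the plan says.** Four places in the protocol deal with bleeding disorders and blood-thinning drugs.

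- **Exclusion criteria, item 4**: "Patients with bleeding disorders and who have been on anticoagulant or antiaggregant treatments".
- **Project Synopsis**, paragraph on clinical evidence of decompensated disease: "Patients with other forms of bleeding disorder, as well as those on anticoagulant or antiaggregant treatments are not eligible to participate in the trial".
- **Background Information of the investigational product**: says that tocotrienols may slow clotting in patients with bleeding disorders, says separately that they may interact with warfarin and with antiaggregants such as aspirin, and concludes "Thus, we advise against taking the treatment with these medications".
- **Algorithm of diagnosis, list of exclusions**: joins the two conditions with *and*, as item 4 does, but puts a comma before it.

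Item 3 of the exclusion criteria has the same construction for another pair: a BMI of 30 kg/m² "or more) and with metabolic syndromes". The Project Synopsis uses the same conjunction ("we propose to exclude the subjects who are obese", continuing after the BMI definition with "and with metabolic syndrome (based on the harmonised criteria) to minimise the risk of misclassification between AFLD and NAFLD"), and so does the diagnostic algorithm.

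**The concern.** Screening staff work from the numbered exclusion list. If they read item 4 as a joint condition, it does not exclude a candidate on warfarin who has no bleeding disorder, or one with a bleeding disorder who takes no such drug. The protocol's own background section attaches a bleeding risk to each of these patients.

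There is a smaller cost to the analysis. The section on withdrawal criteria allows a participant to be discontinued when ineligibility is discovered after entry, and says that withdrawn subjects are not replaced. The sample size section calculates 10 per group and enrols 13, a margin of 13 − 10 = 3 per group that is already set aside for 20% loss to follow-up. A patient admitted on one reading of item 4 and removed on the other would use up part of that margin.

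**Working it through.** No formula applies. The check is to set the sections side by side and ask whom each one excludes.

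**Item 4 against the Project Synopsis.** Two yes/no conditions give four kinds of candidate:

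| Bleeding disorder | On anticoagulant or antiaggregant | Item 4, literal reading | Project Synopsis |
|---|---|---|---|
| yes | yes | excluded | excluded |
| yes | no | not excluded | excluded |
| no | yes | not excluded | excluded |
| no | no | not excluded | not excluded |

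The two differ in the middle rows, that is, for everyone with exactly one condition. The Synopsis leaves no doubt, because it adds the drug users as a further group ("as well as those on anticoagulant or antiaggregant treatments are not eligible to participate in the trial").

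**Is the literal reading a reasonable one?** The list's own drafting supports it. Item 4 uses *or* between anticoagulant and antiaggregant, and items 5 and 12 use *or* for alternatives. Inclusion item 2 uses *and* for two conditions that the same patient must meet. Someone who reads the lists consistently would take item 4 as requiring both.

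**Does another numbered item close the gap?**
- Item 13 lists excluded medications. It names long-term NSAIDs, which might be taken to cover long-term aspirin, but not anticoagulants or antiaggregants as classes, and so not warfarin.
- Item 11 lets the investigator exclude for severe cardiovascular and other disease, and item 16 for any reason in the investigator's judgment. Both are decided case by case, and neither is a rule on these drugs.

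Item 4 is therefore the only numbered criterion aimed at this risk.

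**Does the diagnostic algorithm settle it?** No. The comma leans towards two groups, but the conjunction stays.

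**Item 3.** The exclusion list, the Synopsis and the algorithm all join obesity and metabolic syndrome with *and*, and no section says that one alone is enough. The wording is consistent, but its meaning is left open. The stated purpose is "to minimise the risk of misclassification between AFLD and NAFLD", and the Synopsis links NAFLD to obesity and also to metabolic dysfunction, so the choice between both and either affects who enters. Item 2c excludes NAFLD in its own right, and the algorithm lists BMI, fasting glucose, blood pressure, total cholesterol, triglyceride and HDL for that assessment. This does not say how item 3 is to be read.

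**The case against.** The strongest defence is that item 4 is only loosely drafted. Its words can be read as a list of two groups, each excluded. The Synopsis points that way, the background section gives a separate reason for each group, and the algorithm's comma separates them. A conflict arises only on the one reading that defeats the criterion's evident purpose. Much of this stands: the likely intent can be recovered, and it would be wrong to say that the protocol sets out to admit patients it considers at risk. It does not remove the point, because the recovery depends on background text that a screener need not consult.

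A reader might also infer that item 3 contradicts the Synopsis or the safety warning, or that the protocol leaves NAFLD unguarded. The documents do not support this. The Synopsis uses the same conjunction for that pair, the warning concerns bleeding and says nothing of obesity or metabolic syndrome, and item 2c excludes NAFLD directly.

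**Conclusion.** The point holds for item 4. On its literal reading, the operative criterion conflicts with the Project Synopsis and does not match the separate bleeding warnings in the background section. No other numbered item makes up the difference. This rests on the literal reading being one that site staff could reasonably adopt, which the list's own use of *and* and *or* makes plausible. It does not show that any such patient has been or will be enrolled.

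Its size cannot be put in numbers. The affected candidates are those with exactly one of the two conditions, and the protocol gives no prevalence for them.

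Item 3 is a request for clarification and no more. Its effect cannot be sized either: no prevalences are given, and since the Synopsis says that obese people are more likely to develop metabolic syndrome, the two cannot be treated as independent.

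**What to change.** Reconcile the Project Synopsis, the background section, the diagnostic algorithm and exclusion item 4, so that the numbered list states as clearly as the Synopsis does whether each condition excludes on its own. Two separately numbered criteria, one for bleeding disorders and one for anticoagulant or antiaggregant treatment, would express the Synopsis wording; the algorithm should then carry the same text. Which rule applies is for the sponsor and the responsible clinicians to confirm.

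For item 3, the sponsor should state whether both obesity and metabolic syndrome, or either alone, is required for exclusion, and use that wording in all three places.

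The cost is an edit to the wording of two criteria and the matching text elsewhere. If sites have been applying the literal conjunction in item 4, a separate-criteria wording might add a few screening failures. Patients already enrolled should be checked against the clarified text.

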### **Withdrawal criteria**

During the course of the trial a subject may choose to withdraw early from the trial treatment at any time. This may happen for a number of reasons, including but not limited to:

- The occurrence of what the participant perceives as an intolerable adverse event (AE).
- Inability to comply with trial procedures
- Participant decision

Subjects may choose to stop their participation, and it will not affect their treatment at UKM-affiliated hospitals and clinics in any way. Without losing any of their rights as patients, they will not be penalised and can still continue with the standard treatment available and for follow-up visits at UKMMC. The data and samples already collected would not be used in the final study analysis and would be discarded.

In addition, we may discontinue a participant from the trial treatment at any time if we consider it necessary for any reason including, but not limited to:

- Pregnancy
- Ineligibility (either arising during the trial or retrospectively having been overlooked at screening)
- Significant non-compliance with treatment regimen or trial requirements
- An adverse event which requires discontinuation of the trial medication or results in inability to continue to comply with trial procedures

- Disease progression which requires discontinuation of the trial medication or results in inability to continue to comply with trial procedures

We have adjusted our sample size calculation for this study by considering the risk of dropout among the subjects. Hence, the withdrawn subjects will not be replaced while ensuring that the minimal sample size of this study is achieved. The type of withdrawal and reason for withdrawal will be recorded in the CRF. If the participant is withdrawn due to an adverse event, we will arrange them for follow-up visits at our clinic until the adverse event has resolved or stabilised.

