### Primary Outcome Measures:

1. Change from baseline in Liver Enzyme Profile (Aspartate Aminotransferase [AST], Alanine Aminotransferase [ALT], and Gamma-Glutamyl Transferase [GGT]) at 3 and 6 months. Measured in units per liter (U/L) and reported as absolute and percentage change. Lower values indicate improved liver function.
2. Between-group difference in Liver Enzyme Profile (AST, ALT, GGT) at 3 and 6 months (Tocotrienol-Rich Fraction vs placebo). Measured in U/L. Lower values indicate improvement.
3. Change from baseline in Fatty Liver Index (FLI) at 3 and 6 months. Unitless score (range 0–100). Higher scores indicate greater hepatic steatosis (worse outcome). Reported as absolute and percentage change.
4. Between-group difference in Fatty Liver Index (FLI) at 3 and 6 months (Tocotrienol-Rich Fraction vs placebo). Range 0–100. Higher scores indicate worse steatosis.
5. Change from baseline in Liver Stiffness Measurement using Transient Elastography (FibroScan® score) at 3 and 6 months. Measured in kilopascals (kPa; typical range 2–75). Higher values indicate greater fibrosis. Reported as absolute and percentage change.
6. Between-group difference in Liver Stiffness Measurement (FibroScan® score) at 3 and 6 months (Tocotrienol-Rich Fraction vs placebo). Measured in kPa. Higher values indicate worse fibrosis.

\*Aspartate aminotransferase (AST) is usually used to detect liver damage. It is often ordered in conjunction with other liver enzymes, alanine aminotransferase (ALT) and gamma-glutamyl transpeptidase (GGT), or as part of a liver panel or comprehensive metabolic panel (CMP) to screen for and/or help diagnose liver disorders. The changes in these liver enzymes can also be used to monitor the compliance of patients toward alcohol abstinence.

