## SAMPLE SIZE CALCULATION

Sample size calculation was based on the comparison of two means derived from the effects of tocotrienol on fatty liver index (FLI) in patients with non-alcoholic fatty liver disease (NAFLD) (21). This is because the effectiveness of tocotrienol in alcoholic hepatitis has not been evaluated previously.

Formula of calculating sample size in clinical trial (22):

$$n = [(Z\alpha/2 + Z\beta)^2 \times \{2(\sigma)^2\}] / (\mu_1 - \mu_2)^2$$

Where:

$n$  = sample size required in each group

$\mu_1$  = mean of FLI for tocotrienol group = 12.82  $\mu_2$  = mean of FLI for placebo group = 3.86

$\sigma$  = standard deviation = 7.0

$Z\alpha$ : This depends on level of significance, for 5% this is 1.96  $Z\beta$ : This depends on power, for 80% this is 0.84

$$n = [(1.96 + 0.84)^2 \times \{2(7.0)^2\}] / (12.82 - 3.86)^2$$

The sample size calculated is 10 per group. Taking into account 20% of subjects might be lost to follow up, the number of each group is adjusted to 13. Hence, the total sample size required for this study is 26 individuals.

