### **“Stopping rules” or “discontinuation criteria**

The participation of the trial subjects will be terminated if they cannot adhere to alcohol abstinence and cannot comply with the treatment regimes. Failure to adhere is a serious problem that not only affects the subjects but also the overall conduct and outcome of the research. They will also be stopped from participating in situations where the risks outweigh the anticipated benefits, in cases of severe allergic reactions or any adverse events that occurred in individual trial subjects. Subjects in these trials should be particularly closely monitored and should be withdrawn if they appear to be unduly distressed.

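### Data from participants who stop are to be discarded, which excludes randomised people for reasons that may relate to outcome and contradicts other parts of the protocol

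*Protocol*

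**What the plan says.** In the Withdrawal criteria, the paragraphs on participants who choose to stop list three example reasons: an adverse event that the participant finds intolerable, inability to comply with procedures, and personal decision. They end: "The data and samples already collected would not be used in the final study analysis and would be discarded". A separate paragraph then lists reasons for which the investigator may discontinue a participant, including significant non-compliance, adverse events and disease progression. It says nothing about what happens to those participants' data. The section closes by saying that the sample size allows for dropout, so "the withdrawn subjects will not be replaced while ensuring that the minimal sample size of this study is achieved".

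The section on stopping rules and discontinuation criteria adds: "The participation of the trial subjects will be terminated if they cannot adhere to alcohol abstinence and cannot comply with the treatment regimes". The note under Exclusion criteria makes abstinence compulsory throughout.

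The Primary Outcome Measures include AST, ALT and GGT. The footnote there says: "The changes in these liver enzymes can also be used to monitor the compliance of patients toward alcohol abstinence".

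Four other places point the opposite way from the discard sentence:

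- The source-data section requires records of all pertinent observations on each participant and retention of essential documents.
- Treatment of Subjects says that all data are collected and analysed at six months.
- Reporting Procedures for Adverse Events puts every adverse event on the CRF.
- The Withdrawal criteria themselves put the type and reason of withdrawal on the CRF and follow adverse events until they resolve or stabilise.

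Nowhere does the protocol say that all randomised participants will be analysed.

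**The concern.** Randomisation protects a comparison only while everyone randomised stays in it. The discard rule drops people after randomisation, and the listed reasons are not neutral. Intolerance may be related to the product. In this trial inability to comply may mean a return to drinking, which bears on the liver outcomes. If departures differ between arms, or depend on how well a participant is doing, those who remain are no longer comparable. The bias can go either way.

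The enzyme footnote adds a second route. A rise in AST, ALT or GGT may be read as evidence of drinking, and drinking is a ground for ending participation. Removal related to a primary outcome is therefore permitted, though not prescribed.

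This cannot be left to a statistical analysis plan. A plan can define analysis sets, but it cannot recover data and samples already discarded. With 13 per arm, each person dropped is about 8% of an arm (1/13).

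**Working it through.** **1. The protocol's own figure.** The Sample Size Calculation gives "mean of FLI for tocotrienol group = 12.82", "mean of FLI for placebo group = 3.86", SD 7.0, and normal quantiles ("for 5% this is 1.96", "for 80% this is 0.84"). The difference is 12.82 − 3.86 = 8.96, or 8.96/7 = 1.28 SD. I read it as points of improvement, since a lower FLI is better.

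n = (1.96 + 0.84)² × 2 × 7.0² / 8.96² = 7.84 × 98 / 80.28 = 9.57, so 10 per group. With 20% loss, 10/0.8 = 12.5, so 13 per group and 26 in total. The stated sample size reproduces.

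**2. Power with and without the lost participants.** Two-sided t-test at 5%, noncentrality 1.28 × √(n/2), 2n − 2 degrees of freedom:

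- 13 per arm: noncentrality 3.26, 24 df, power 87.9%.
- 10 per arm: noncentrality 2.86, 18 df, power 77.2%.

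The first figure requires complete six-month data on everyone and an effect that relapse does not dilute.

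**3. What selective loss could do.** The documents give no removal rate by arm and no link between removal and outcome, so both are assumptions. FLI is used because it is the only outcome with a stated difference and SD. The model has 13 per arm, SD 7, 40,000 simulated trials per setting, and a t-test on those who remain. Each participant has a removal score −ρ × (standardised improvement) + √(1 − ρ²) × (independent noise) and is removed above a threshold. Here ρ is the correlation between removal score and poor outcome.

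(a) Equal 20% removal in each arm, not depending on treatment, ρ from 0 to 0.7: the difference is unbiased and type I error stays at about 5%.

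(b) True difference 8.96, one threshold for both arms, 20% removed overall:

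| ρ | Removed, tocotrienol / placebo | Estimated difference | Power |
|---|---|---|---|
| 0 | 20% / 20% | 9.0 | 78% |
| 0.3 | 14.7% / 25.3% | 8.6 | 76% |
| 0.5 | 11.4% / 28.6% | 8.1 | 73% |
| 0.7 | 8.4% / 31.6% | 7.2 | 68% |

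Removal becomes unequal by itself because placebo participants do worse. The shrinkage at ρ = 0.3, 0.5 and 0.7 is about 4%, 10% and 19%. The first row shows that loss of numbers alone takes power from 88% to 78%; selection accounts for the rest.

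(c) No true difference, 10% removed in one arm and 30% in the other: at ρ = 0.3, 0.5 and 0.7 a spurious difference of 0.6, 1.0 and 1.5 points appears, with type I error 5.3%, 6.2% and 7.7%. At 0% against 40% the spurious difference is about 1.3, 2.3 and 3.2 points, with type I error about 6.5%, 10% and 16%.

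(d) Direction: with a true difference of 8.96, if tocotrienol loses 30% and placebo 10%, the estimate rises to 9.6, 10.0 and 10.4 at the same three correlations. With the rates reversed it falls to 8.3, 7.9 and 7.5.

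**The case against.** The discard sentence belongs to the text on voluntary withdrawal. Removal for non-abstinence is a termination by the trial team, and no section says that those participants' data are discarded. A reader might infer that everyone who drinks is deleted from the analysis, but the document leaves this open. What stands is that inability to comply is itself a listed voluntary reason, and that the no-replacement text counts withdrawn participants against the dropout allowance. The scope therefore needs stating.

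A reader might also infer that high enzymes lead to removal and then to deletion of those same values. The footnote says only that the enzymes can be used for monitoring. It sets no threshold and makes no link to termination. Treatment of Subjects answers non-adherence with monitoring, counselling and pharmacotherapy.

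Nor can it be said that adverse events behind withdrawals would vanish from the safety data, because other passages require them to be recorded and followed. The passages conflict, and it is not established that the discard sentence prevails.

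On size, much larger distortions can be produced by assuming a sharp cut on the outcome itself. At 1.28 SD, removing the worst 20% or 30% of placebo by a common cut shrinks the effect by 24% or 32%. Nothing in the protocol describes such a cut. Ordinary attrition would also cost power without any discarding, and keeping data up to withdrawal does not restore missing six-month values. The 88% is thus an upper bound, not a promise.

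None of these arguments gives a reason to discard data already collected.

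**Conclusion.** The concern holds in this form: the protocol affirmatively orders data from voluntary withdrawers to be discarded, leaves the rule's reach to other removed participants unstated, and contradicts its own passages on records, adverse events and analysis. The comparison could become one of selected completers; the text does not make that certain. Outcome-related removal through the enzymes is allowed but not prescribed.

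Under the stated assumptions the possible effect runs from no bias (equal, treatment-independent removal) to a loss of about 4% to 19% of the planned FLI difference under a common threshold removing 20%. Type I error reaches 5.3% to 7.7% with 10% against 30% removal, and more with greater imbalance. Even without bias, the result would describe only those who stayed in. The protocol should be corrected because discarding is irreversible and the arms are small.

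**What to change.** - Delete the discard sentence. Keep and analyse all data collected up to withdrawal unless the participant withdraws consent to their use.
- State that all randomised participants are analysed in their assigned arm using every available visit, with the abstinent and compliant subset as a sensitivity analysis.
- Report adverse events for everyone who took a capsule.
- Do not use AST, ALT or GGT as the basis for judging abstinence. Use the alcohol questionnaire already in the trial at the existing 3- and 6-month visits. The Abstract mentions alcohol questionnaires without timing, and the AUDIT is described under Screening.
- Reconcile the stopping rules, Withdrawal criteria, source-data section, Treatment of Subjects and adverse event reporting on what ends participation and what then happens to the data. Which clinical stopping rule is right is not judged here.

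The cost is a protocol amendment, matching consent wording and a short questionnaire at two visits that already take place. No additional participants are needed for this change. The protocol speaks of recruitment in the past tense, so some people may have enrolled under the discard promise and may need to be re-consented. Including those who relapse may dilute the estimated effect.
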